### **Selection, Training and Supervision of Interventionists (Stage 2 & 3)**

Selection. Interventionists will be doctoral trainees. Training and supervision procedures are detailed below.

Training. Interventionists will receive intensive training which will consist of (a) a 2-day training workshop on MI with Drs. [name] and [name], (b) reviewing tapes and model BMI sessions from previous research, (c) individual reading of the intervention manual, (d) digitally recorded mock interviews followed by individual feedback and evaluation, and (e) weekly group supervision and tape review with [name]. Therapists will be deemed ready after completing a mock session rated as acceptable by Consultant [name].

Supervision. Treatment providers will attend weekly supervision meetings with [name]. These meetings will be supplemented with monthly phone supervision with [name]. All sessions will be digitally recorded. The PI will listen to 30% of the sessions, randomly selected, and will review for use in ongoing supervision. In addition, [name] will listen to one randomly chosen session per interventionist per month and complete the Motivational Interviewing Treatment Integrity Code (MITI) and relevant adherence questionnaire. During individual phone supervision sessions, [name] will provide feedback to interventionists based on her review of session tapes. This follows fidelity procedures that we have used previously (R01AA016564; [name]).

## **5.0 Local Number of Subjects**

5.1 *Indicate the total number of subjects that will be enrolled or records that will be reviewed locally.*

Response: The total number of participants across the three studies will be 128.

5.2 *If applicable, indicate how many subjects you expect to screen to reach your target sample.*

Response: 175

5.3 *Justify the feasibility of recruiting the proposed number of eligible subjects within the anticipated recruitment period. For example, how many potential subjects do you have access to? What percentage of those potential subjects do you need to recruit?*

Response: Participants will be recruited from the nearly a dozen colleges in the greater Buffalo area. The University at Buffalo alone has over 30,000 students, approximately ½ of whom are women. Given the large student population from which we will draw from, and the fair financial remuneration that participants will receive for participation, achieving our target N within the proposed timeframe is highly feasible.

## **6.0 Inclusion and Exclusion Criteria**

6.1 *Describe the criteria that define who will be included in your final study sample.*

Response: We will recruit heavy drinking (i.e. 4 or more drinks in a single sitting, 2 or more times monthly in past 3 months) college women who are between 18 and 24 years old, enrolled in a part or full-time in a 4-year degree program. For Studies 2 and 3, women will be recruited in dyads, and both members of the dyad must be willing to participate. The friends in the dyad must go out together at least once a week. Women must be proficient in the English language. This is unlikely to pose a challenge, as they are enrolled in U.S., English-speaking universities. There are no other inclusion or exclusion criteria.

6.2 *Describe the criteria that define who will be excluded from your final study sample.*

Response: See above. There are no other exclusion criteria.

6.3 *Indicate specifically whether you will include any of the following special populations in your study using the checkboxes below.*

**NOTE: Members of special populations may not be targeted for enrollment in your study unless you indicate this in your inclusion criteria.**

Response: No members of these special populations will be targeted to enrollment.

6.4 *Indicate whether you will include non-English speaking individuals in your study. Provide justification if you will exclude non-English speaking individuals.*

Response: All participants in the study must be proficient in English.

## 7.0 Vulnerable Populations

*If the research involves special populations that are considered vulnerable, describe the safeguards included to protect their rights and welfare.*

**N/A:** This research does not involve pregnant women.

7.1 *For research that involves neonates of uncertain viability or non-viable neonates, safeguards include:*

*NOTE CHECKLISTS: Non-Viable Neonates (HRP-413), or Neonates of Uncertain Viability (HRP-414)*

**N/A:** This research does not involve non-viable neonates/neonates of uncertain viability.

7.2 *For research that involves prisoners, safeguards include:*

*NOTE CHECKLIST: Prisoners (HRP-415)*

**N/A:** This research does not involve prisoners.

7.3 *For research that involves persons who have not attained the legal age for consent to treatments or procedures involved in the research ("children"), safeguards include:*

*NOTE CHECKLIST: Children (HRP-416)*

**N/A:** This research does not involve persons who have not attained the legal age for consent to treatments or procedures ("children").

7.4 *For research that involves cognitively impaired adults, safeguards include:*

*NOTE CHECKLIST: Cognitively Impaired Adults (HRP-417)*

**N/A:** This research does not involve cognitively impaired adults.

7.5 *Consider if other specifically targeted populations such as students, employees of a specific firm, or educationally or economically disadvantaged persons are vulnerable. Provide information regarding their safeguards and protections, including safeguards to eliminate coercion or undue influence.*

Response: There is no specific targeting of any population in this study. The original sample was a community sample, drawn to be representative of the greater-Buffalo community.

## 8.0 Eligibility Screening

8.1 *Describe screening procedures for determining subjects' eligibility. Screening refers to determining if prospective participants meet inclusion and exclusion criteria.*

- Include all relevant screening documents with your submission (e.g. screening protocol, script, questionnaire).*

We will recruit heavy drinking (i.e. 4 or more drinks in a single sitting [HED] 2 or more times monthly in past 3 months) women into our sample. For phase 2 and 3, members of the dyad must also go out together at least once a week. These women will be recruited via campus and community-wide advertisements for a study of "women's social experiences". Telephone screens will be used to determine eligibility.

## 9.0 Recruitment Methods

9.1 *Describe when, where, and how potential subjects will be recruited.*

Friend dyads will be recruited in pairs via campus and community-wide advertisements for a study of women's social experiences. Those interested will call in for a telephone screening to determine eligibility. To be eligible for the study, both women in the dyad must report heavy episodic drinking (i.e. 4 or more drinks in a single sitting, HED) at least twice monthly for the past 3 months. In addition, the friends must report that they go out together regularly (at least once weekly). Eligible participants will be scheduled for a focus group session (for Stage 1) or for an intervention session (for Stages 2,3). At the focus group or intervention session, women will be provided with an overview of study procedures and what their involvement will entail. They then will be given the opportunity to ask questions. Following this, informed consent will be obtained.

9.2 *Describe how you will protect the privacy interests of prospective subjects during the recruitment process.*

Response: All potential participants will be contacted privately, via email and/or phone. All screenings will be conducted over the telephone.

9.3 *Identify any materials that will be used to recruit subjects.*

*NOTE: Examples include scripts for telephone calls, in person announcements / presentations, email invitations.*

- For advertisements, include the final copy of printed advertisements with your submission. When advertisements are taped for broadcast, attach the final audio/video tape. NOTE: You may submit the wording of the advertisement prior to taping to ensure there will be no IRB-required revisions, provided the IRB also reviews and approves the final version.*

Response: See attached advertisement/recruitment flyer.

Facebook Ads will be posted on Facebook using stock/royalty-free images downloaded from Shutterstock (<https://www.shutterstock.com/>), a website that provides stock photography.

Each ad that posted on Facebook has three components: 1) Headline (25-character limit), 2) Image, and 3) Text (125-character limit). For the proposed recruitment campaign, each image that will appear on Facebook will be accompanied using the headlines and study descriptions detailed below, or using equivalent language.

### 1. Ad Headlines

Due to the character limit, headlines will not be used

## 2. Ad Images

## 3. Compliance with Advertising Standards

The images that will be used will not be targeting minors, and are compliant with Facebook policy ([https://www.facebook.com/policies/ads/prohibited\\_content](https://www.facebook.com/policies/ads/prohibited_content)).

## 4. Ad Recruitment Information

Each ad will use equivalent language to communicate that:

The University at Buffalo is recruiting women ages 18-24 who are in college.

Investigators from the Department of Psychology at the University at Buffalo are looking for women to help us evaluate a new program designed for friends to help protect one another against sexual assault. Participation will take approximately 4 hours of your time (across four weeks) and you will each earn up to \$50 in cash.

INTERESTED?? Please Call [contact] or email us at [contact]

## 10.0 Procedures Involved

10.1 *Provide a description of all research procedures or activities being performed and when they are performed once a subject is screened and determined to be eligible. Provide as much detail as possible.*

Response: See procedures described above.

10.2 *Describe what data will be collected.*

*NOTE: For studies with multiple data collection points or long-term follow up, consider the addition of a schedule or table in your response.*

Response: Please see description provided above.

 10.3 *List any instruments or measurement tools used to collect data (e.g. questionnaire, interview guide, validated instrument, data collection form).*

### **Instruments & Measures (For Stage 3)**

Data collection will occur at baseline and bi-weekly assessments, and a final evaluation that will be administered at the end of the last bi-weekly assessment. At baseline, we will collect demographic data, as well as drinking and sexual victimization history, and descriptive information regarding the relationship of the friends in our dyads. Other self-report measures will be administered both at baseline and then weekly during the follow-up periods (as denoted below). In the final (exit interview) evaluation, we will obtain feedback on participants' perceptions of the intervention and potential iatrogenic effects. All self-report measures may be completed prior to the session.

The proposed intervention will be designed to use relationship and responsibility in friend dyads as the basis for decreasing perceived barriers to intervention, improving readiness for helping friends, increasing knowledge about alcohol's effects on helping and strategies for overcoming or working around these effects, and imparting friend-based helping skills. These attitudes and behaviors will be the target intervention outcomes. Sexual assault will be examined as a secondary outcome. Changes in drinking also will be examined though this is not the principal focus of the intervention.

#### **Baseline Assessment**

*Demographic (baseline).* Demographic variables will be assessed, including sex, age, ethnicity, sexual orientation, family history of alcohol problems, living situation (with family, friends, alone, etc), work status, year in school, romantic relationships, and weight (for BAC calculations).

*Sexual Assault (baseline).* A revised version of the Sexual Experiences Survey (RSES; Koss et al., 2007; will be used to measure a spectrum of sexual victimization experiences. At baseline, lifetime experiences will be assessed. This will enable us to examine whether SA history affects intervention efficacy, or intervention response (e.g., guilt, blame, other possible iatrogenic effects) in exploratory analyses.

*Drinking history (baseline).* A variety of alcohol behaviors and related outcomes will be assessed. Using a grid-based average assessment measure, participants will report on typical weekly alcohol consumption over the past week (for relevant comparison of follow-up data) and past year (for descriptive purposes), including the average number of drinks consumed per occasion, and the average time over which drinks were consumed (for blood alcohol calculations). Harmful drinking outcomes will be assessed with the 48-item Young Adult Alcohol Consequences Questionnaire (YAACQ; [name] et al., 2006, 2007). We will also assess frequency of drinking in various contexts including parties, bars, etc. to assess patterns of exposure to high risk contexts.

*Relationship information (baseline).* We will assess the duration and origin of the friendship, as well typical amount of time spent together. Note that at baseline we will assess level of closeness to confirm eligibility. Dyads who do not identify one another as a "close friend" will be excluded from participation.

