**Stage 3 Procedures:**

*Intervention: FMI Mini-Controlled Trial with Intensive Follow-Up*

In this stage, we will test the finalized FMI (see **Screening, Eligibility, and Recruitment** above). To do this, we will contrast outcomes among those in this trial (N=24 dyads) with 24 pairs of friend dyads (total dyad N=48) who are randomly assigned to a wait list control condition.

The FMI will consist of a single session. Sessions will be offered on many days and times across the week to accommodate variability in student schedules. Each session will begin with a baseline assessment. In this session, women will be provided with the refined intervention protocol and will have the opportunity to role play and practice implementing the skills and strategies. Following the intervention, participants will be encouraged to utilize the skills and strategies presented in the intervention over the next 12 weeks, whenever they are out with their friend in a social context.

Dyad pairs assigned randomly (stratified on drinking levels, sexual assault history, and age) to the wait list control condition will be assessed once at baseline and again 12 weeks post-baseline. Assessment measures (baseline, 12 weeks) will mirror those administered to women in the FMI condition. At the completion of the 12 week “wait list,” participants will be administered the FMI and followed for 12 weeks. Comparison of outcomes across conditions will allow for stronger inferences about the efficacy of the intervention, will allow for examination of measurement reactivity, and will increase our sample size to examine within person change.

*Follow-up Assessments.* We will conduct bi-weekly online post-intervention assessments (with the first assessment to occur within 2 weeks of FMI completion) for 12 weeks. The bi-

weekly structure will optimally capture women's experiences applying strategies from the intervention. Participants will be reminded of follow-up assessments by phone, text, and email prompt. Individual members of the dyad will be interviewed in the unlikely event that the other member is lost to follow up over the brief follow-up period. At the end of the 12 weeks, participants will be contacted for an exit interview.

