Brief Intervention Adherence Checklist. Following prior MI studies (Barnett et al. 2007; Murphy et al., 2010), 25% of the interviews will be selected randomly for review by [name]. Two aspects will be assessed, Content and MI Adherence. [name] will complete a 52-item checklist based on the FMI components (*content*), to evaluate whether each intervention component was covered (Moyers et al., 2010), as well as the MITI (below) for each session to determine whether interventionists maintain MI proficiency.

Motivational Interviewing Treatment Integrity Code Version 3.1.1 (MITI 3.1.1; Moyers et al., 2010) The MITI evaluates interventionist adherence to MI principles. Randomly-selected 20-minute segments of the session are coded. The MITI contains global and behavior components. The global ratings are (a) evocation; (b) collaboration; (c) autonomy/support; (d) direction; (e) empathy; (f) acknowledging change talk; and (g) inviting change talk. The behavior counts assess (a) MI adherent (e.g., emphasizing self-efficacy) and MI non-adherent (e.g., confronting) behaviors; (b) the types of questions; (c) types of reflections, and (d) providing information. As the FMI is built on a MI framework, it is crucial to examine therapist interactions to evaluate the level of collaboration, empathy, and autonomy/support infused through the session interaction. As MI focuses on attaining high ratings in these areas as more predictive of behavior change (Miller & Rollnick, 2012), our ability to evaluate if and how well the therapists delivered these skills is a crucial aspect of intervention fidelity.

Relationship Quality

Effects on the relationship are among the primary concerns that women cite regarding intervening in potential assault situations. Thus, we will examine whether the intervention has any influence on the relationship quality. Further, given that relationship and responsibility are strong predictors of helping behavior, we also will examine these as potential moderators of intervention outcome in exploratory analysis.

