Our burst design provides a rich opportunity to examine whether changes in target constructs of interest (e.g., barriers, skills, alcohol knowledge and strategies) are associated with implementation of FAPBs. For these analyses we will combine the post-intervention data from our FMI and WLC groups after the latter has completed the intervention and follow-up assessments. Combining groups will increase our sample size and provide more stable estimates of effect sizes. For these analyses we will include reports of past week protective behavioral strategies just prior to the intervention and weekly aggregates of protective behavioral strategies from our three-month follow-up yielding 7 repeated measures nested within individuals and individuals nested within dyads. Using growth models, we will model change in readiness, perceived barriers, alcohol knowledge and strategies, and implementation of FAPBs. Effect sizes characterizing change will be computed in two ways: 1). Computing a difference score using baseline and the first follow-up divided by the standard deviation of the difference score, and 2). A difference score using baseline and the last assessment of the follow-up divided by the standard deviation of the difference score (Gibbons et al., 1993; Morris & DeShon, 2002). Individual level intercepts and slopes will be output from these growth models and this will allow us to examine correlations between slopes and intercepts. We expect that reductions in perceived barriers (better self-efficacy, fewer interpersonal concerns), and increases in readiness will be positively related to implementation of FAPBs. Our growth models will

also allow us to include individual characteristics (e.g. assault history, drinking history, relationship, responsibility) to examine their association with change in perceived barriers, skill implementation, etc. (e.g., prior history of sexual assault is related to more or less change in variables our intervention is expected to impact).

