A prominent feature of our design is that individuals are nested within dyads, and this necessitates a data analytic approach that can accommodate nested data structures. Hence, our Aim 3 analyses are built around hierarchical linear models (HLMs). First, we will evaluate group differences on variables from our first post-intervention assessment (i.e. perceived barriers, readiness, alcohol knowledge and strategies, and implementation of FAPBs) using a two level model (individuals nested within dyads). Treatment will be dummy coded (FMI vs. waitlist control group) and included as a level two covariate. Second, we will utilize all data from our three month follow-ups and repeat these analyses using a three-level model (6 repeated measures nested within individuals, and individuals nested within dyads). In these models treatment will be included as a level three covariate. We will use  $\beta$  to describe effect sizes (Cohen, 1988; Selya et al., 2012).

Our burst design provides a rich opportunity to examine whether changes in target constructs of interest (e.g., barriers, skills, alcohol knowledge and strategies) are associated with implementation of FAPBs. For these analyses we will combine the post-intervention data from our FMI and WLC groups after the latter has completed the intervention and follow-up assessments. Combining groups will increase our sample size and provide more stable estimates of effect sizes. For these analyses we will include reports of past week protective behavioral strategies just prior to the intervention and weekly aggregates of variables of interest from our three-month follow-up yielding 7 repeated measures nested within individuals and individuals nested within dyads. Time will be included as a level-1 covariate, and we will

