examine change in readiness, perceived barriers, alcohol knowledge and strategies, and implementation of FAPBs. Effect sizes characterizing change will be computed in two ways: 1). Computing a difference score using baseline and the first follow-up divided by the standard deviation of the difference score, and 2). A difference score using baseline and the last assessment of the follow-up divided by the standard deviation of the difference score (Gibbons et al., 1993; Morris & DeShon, 2002). Individual level intercepts and slopes will be output from these models and this will allow us to examine correlations between slopes and intercepts. We expect that reductions in perceived barriers (better self-efficacy, fewer interpersonal concerns), and increases in readiness will be positively related to implementation of FAPBs. Our models will also allow us to include individual characteristics (e.g. assault history, drinking history, relationship, responsibility) to examine their association with change in perceived barriers, skill implementation, etc. (e.g., prior history of sexual assault is related to more or less change in variables our intervention is expected to impact).

In exploratory analyses, we will examine whether increases in implementation of FAPB from baseline to follow-up are associated with rates of sexual victimization. For these analyses we collapse our follow-up data into dichotomous variable indicating whether sexual victimization occurred. Using a two-level HLM (individuals nested within dyads), this dichotomous outcome will be regressed on the intercepts and slopes of FAPBs (described above). Steeper increases in FAPBs are expected to be associated with lower likelihood of sexual victimization at follow-up controlling for baseline levels of sexual victimization. Odds ratio will be used to describe the effect size. Data from stakeholder and exit interviews will be analyzed using qualitative data analytic techniques.

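### Exploratory moderator questions about FMI efficacy are matched only to an analysis of pooled, all-treated data, which cannot separate effect modification from change that would have occurred untreated

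*Combined protocol and SAP*

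**What the plan says.** Two places in protocol section 10.3 pose a question about efficacy.

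- Under Baseline Assessment, on lifetime sexual assault history: "This will enable us to examine whether SA history affects intervention efficacy". The sentence goes on to responses such as guilt and blame, and labels the work exploratory.
- Under Relationship Quality, on relationship and responsibility: "we also will examine these as potential moderators of intervention outcome in exploratory analysis".

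The analysis that uses these traits is in the growth-model paragraphs of protocol section 16.1 (Aim 3) and in the Outcome analyses of the SAP. Its data set is defined by "we will combine the post-intervention data from our FMI and WLC groups after the latter has completed the intervention". The traits then enter as follows: "Our models will also allow us to include individual characteristics (e.g. assault history, drinking history, relationship, responsibility) to examine their association with change". The example given is whether "prior history of sexual assault is related to more or less change in variables our intervention is expected to impact".

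The models that compare the randomised arms are specified separately: "Treatment will be dummy coded (FMI vs. waitlist control group) and included as a level two covariate". In the three-level version treatment moves to level three. No treatment-by-trait term is stated for either version.

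Stage 3 Procedures (section 4) stratify allocation on drinking levels, sexual assault history and age. They schedule waitlist women for assessment at baseline and again at week 12, before they receive the FMI.

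**The concern.** Whether a trait affects efficacy, or moderates outcome, is a question about the difference between treated and untreated women at each level of the trait. In the combined data set there are no untreated women. A trait that predicts how women change over 12 weeks for any reason, such as natural drift, reaction to repeated measurement or a fading baseline difference, will be associated with change there even if the FMI works equally well for everyone.

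The pilot is meant to supply effect sizes for later studies (section 16.2). If a pooled association were carried forward as moderation, a later study could take women with an assault history to respond more or less to the FMI when the data show only that they changed more or less. The randomised comparison can address the question, but no plan is stated to use it that way.

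**Working it through.** **The plan's own figure.** There is none for a moderator analysis. Section 16.2 gives 88 women for Study 3 without a numeric alpha, power, effect size or within-dyad correlation. The Stage 3 text gives 48 dyads, or 96 women. The range 88 to 96 is used below. All other inputs are assumptions.

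**What each analysis estimates.** Let m be the trait, g the untreated change per unit of m, τ the FMI effect at m = 0, and δ the true effect modification.

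- Mean change, untreated: a + g·m
- Mean change, treated: a + τ + (g + δ)·m
- Trait coefficient in all-treated data: g + δ
- Treatment-by-trait term in the randomised comparison: (g + δ) − g = δ

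The pooled coefficient equals δ only when g = 0. A larger sample does not separate g from δ.

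**How large g could be: one illustration.** Assume women with a history start 0.5 SD lower, the test-retest correlation r is 0.6 or 0.7, and the FMI effect is identical in both groups.

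- If the gap decays towards a common mean, the difference in change is 0.5 × (1 − r): 0.5 × 0.4 = 0.20 SD, or 0.5 × 0.3 = 0.15 SD.
- If the gap is a stable group difference, each woman regresses towards her own group's mean and the difference in change is 0.

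**How often g would look like a moderator.** Simulation with 3,000 runs per setting, 44 or 48 dyads, within-dyad correlation 0.3, trait prevalence 0.3 or 0.5, a constant FMI effect of 0.5 SD and δ = 0, tested at a nominal 5%:

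| g (SD) | Pooled model rejects | Randomised interaction rejects |
|---|---|---|
| 0 | about 5% | 4–5% |
| 0.3 | 26–32% | 4–5% |
| 0.5 | 59–70% | about 5% |
| 0.8 | 94–98% | 4–5% |

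The interaction averaged about zero throughout. The documents do not say which row applies.

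**Precision of the randomised term.** For a woman-level binary trait with prevalence p, residual SD 1 and independent members, SE = √[(4/N)(1/p + 1/(1 − p))].

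- N = 88, p = 0.2: √[(4/88)(6.25)] = 0.53. Detectable difference at two-sided 5% and 80% power: 2.80 × 0.53 ≈ 1.5 SD. Power for 0.5 SD: Φ(0.5/0.533 − 1.96) ≈ 15%.
- N = 96, p = 0.5: √[(4/96)(4)] = 0.41. Detectable difference ≈ 1.1 SD. Power for 0.5 SD: Φ(0.5/0.408 − 1.96) ≈ 23%.
- If both members share the trait and the within-dyad correlation is 0.3, the detectable difference rises to as much as 1.49 × √1.3 ≈ 1.7 SD.

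Residual SD 1 gives no credit for baseline adjustment. With r = 0.6 or 0.7, N = 96 and p = 0.5, adjustment multiplies the SE by √(1 − r²): 0.408 × 0.80 = 0.33, or 0.408 × 0.71 = 0.29. Power for 0.5 SD is then about 33 to 40%, which is still low.

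**The case against.** Four arguments on the other side have force.

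First, a reader might infer that the plan will report a false moderator of efficacy. The documents do not say so. Section 16.1 and the SAP speak of association with change, which is accurate for pooled data. Section 10.3 names no model for its questions. The link to the pooled models rests on there being no other analysis of these traits. What stands is a mismatch between the question and the analysis.

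Second, a reader might infer that the pooled estimate must be non-zero even when the FMI works equally for all. That is not so. Women are not selected on the outcome and assault history is a lifetime trait, so ordinary regression to the mean produces no group difference if the gap is stable. The bias needs a trait that predicts untreated change, and the documents give no evidence of its size.

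Third, part of the question suits the pooled data. Guilt or blame in response to the FMI concerns women who received it. Both questions are labelled exploratory, and no section says that a later trial will be targeted on these traits.

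Fourth, the randomised term is noisy. In the decaying-gap illustration (96 women, half with a history), the pooled SE is √[2(1 − r)(2/48)] = 0.18 or 0.16. Combined with the bias of 0.20 or 0.15, the root mean squared error is 0.27 or 0.22. That is below the SE of 0.33 or 0.29 for the baseline-adjusted interaction. This is correct, but the plan already commits to 95% bands because pilot estimates are unreliable. A wide band around the quantity named in section 10.3 is more useful than a narrower one around a different quantity.

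**Conclusion.** The concern holds in a limited form. Section 10.3 asks whether traits alter efficacy, while the only analysis described for those traits estimates their association with change among treated women. The two agree only if the trait does not predict untreated change. Under the assumed inputs the discrepancy runs from nothing (stable gap) to 0.15 to 0.20 SD (decaying gap, r = 0.7 to 0.6). The rejection rates in the table apply only if g takes the values shown. The analyses are exploratory, and the main FMI-versus-waitlist comparison is not affected. This is an inexpensive improvement to the plan and does not put the trial's main result in doubt.

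**What to change.** Add to the SAP, and align section 10.3 with it:

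1. Fit a week-12 FMI-versus-waitlist model with women nested in dyads, adjusted for the baseline value of the outcome. Add, one at a time and each with the trait's main effect, treatment-by-assault-history, treatment-by-baseline-relationship and treatment-by-baseline-responsibility terms. Week 12 is the time point because, as the waitlist schedule is written, it is the only untreated follow-up.
2. Use baseline trait values only. Responsibility is also measured bi-weekly after randomisation and a shared sense of it is something the FMI seeks to build, so a later value could itself be an effect of treatment.
3. Report each interaction with its 95% band, labelled exploratory and imprecise: about 15 to 23% power for a 0.5 SD subgroup difference under the assumptions above, before any gain from baseline adjustment.
4. Describe the pooled-data associations as predictors of change among treated women, and not as moderators of efficacy.

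The cost is a few sentences and three extra terms per outcome. The data are already scheduled in both arms. The downside is wide intervals, which the report should state.
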